400 participants (75 participants per active vaccine group, 25 in the placebo group) will be randomized in parallel in a 3:3:3:3:3:1 ratio to 1 of 6 vaccination groups. Participants will receive a 2-dose (56-day interval, Groups 1-3) vaccination regimen at different dose levels $(5 \times 10^{10} \text{ vp}, 2.5 \times 10^{10} \text{ vp}, \text{ and } 1.25 \times 10^{10} \text{ vp})$ or single-dose vaccination regimen (Groups 4-5) at different dose levels $(1 \times 10^{11} \text{ vp}, 5 \times 10^{10} \text{ vp})$, or placebo (Group 6). For blinding purposes, participants in the single-dose groups (Groups 4-5) will receive a placebo vaccination on Day 57. Additional exploratory cellular immunogenicity evaluations (PBMC) will be performed in a subset of participants (21/group in Groups 1-5, 7 in Group 6; at selected sites). Participants in Group 6 who received 2-doses of placebo in the primary vaccine regimen will receive 2 doses of active vaccine at a single dose level of $5 \times 10^{10} \text{ vp}$, at a 28-day interval.

Groups 7-8

75 participants (50 participants in the active vaccine group, 25 in the placebo group) will be randomized in parallel in a 2:1 ratio, to 1 of 2 vaccination groups. Participants will receive a 2 dose (28-day interval, Groups 7) vaccination regimen at a 5×10^{10} vp dose level or placebo (Group 8). Participants in Group 8 who received 2-doses of placebo in the primary vaccine regimen will receive 2 doses of active vaccine at a single dose level of 5×10^{10} vp, at a 28-day interval.

Groups 9-10

75 participants (50 participants in the active vaccine group, 25 in the placebo group) will be randomized in parallel in a 2:1 ratio, to 1 of 2 vaccination groups. Participants will receive a 2 dose (84-day interval, Group 9) vaccination regimen at a 5×10^{10} vp dose level or placebo (Group 10). Participants in Group 10 who received 2-doses of placebo in the primary vaccine regimen will receive 2 doses of active vaccine at a single dose level of 5×10^{10} vp, at a 28-day interval.

Vaccination Schedule – Adults

Adults ≥18 to ≤55 Years and ≥65 Years

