400 participants (75 participants per active vaccine group, 25 in the placebo group) will be randomized in parallel in a 3:3:3:3:1 ratio to 1 of 6 vaccination groups. Participants will receive a 2-dose (56-day interval, Groups 1-3) vaccination regimen at different dose levels (5×10^{10} vp, 2.5×10^{10} vp, and 1.25×10^{10} vp) or single-dose vaccination regimen (Groups 4-5) at different dose levels (1×10^{11} vp, 5×10^{10} vp), or placebo (Group 6). For blinding purposes, participants in the single-dose groups (Groups 4-5) will receive a placebo vaccination on Day 57. Additional exploratory cellular immunogenicity evaluations (PBMC) will be performed in a subset of participants (21/group in Groups 1-5, 7 in Group 6; at selected sites). Participants in Group 6 who received 2-doses of placebo in the primary vaccine regimen will receive 2 doses of active vaccine at a single dose level of 5×10^{10} vp, at a 28-day interval.

Groups 7-8

75 participants (50 participants in the active vaccine group, 25 in the placebo group) will be randomized in parallel in a 2:1 ratio, to 1 of 2 vaccination groups. Participants will receive a 2 dose (28-day interval, Groups 7^a) vaccination regimen at a 5×10^{10} vp dose level or placebo (Group 8). Participants in Group 8 who received 2-doses of placebo in the primary vaccine regimen will receive 2 doses of active vaccine at a single dose level of 5×10^{10} vp, at a 28-day interval.

-

^a Group 7 and 8: only 2 subjects (one in each group) are vaccinated at a 28-day interval, due to a study pause

Groups 9-10

75 participants (50 participants in the active vaccine group, 25 in the placebo group) will be randomized in parallel in a 2:1 ratio, to 1 of 2 vaccination groups. Participants will receive a 2 dose (84-day interval, Group 9) vaccination regimen at a 5×10^{10} vp dose level or placebo (Group 10). Participants in Group 10 who received 2-doses of placebo in the primary vaccine regimen will receive 2 doses of active vaccine at a single dose level of 5×10^{10} vp, at a 28-day interval.

The vaccination schedules are presented in Table 2.

Table 2: Vaccination Schedules Adults

Adults ≥18 to ≤55 Years and ≥65 Years

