4.3. Justification for Dose

Adults

The regimen and dose selection in this study are aimed at providing information on safety and immunogenicity of multiple 2-dose and single-dose schedules of the Ad26.COV2.S vaccine, including lower dose levels (ie, 2.5×10^{10} vp, and 1.25×10^{10} vp) compared to the dose levels used in the first-in-human study (VAC31518COV1001). In October 2020, the study was temporarily paused because one of the pausing rules was met in study COV3001. When the pause was lifted, most of the participants in Groups 7-8 had missed their visit window for Vaccination 2 (Visit 4), rendering the intent of the 28-day vaccination interval in these groups futile. The goal in offering 2 doses of study vaccine to those participants who initially received placebo in this study is to recreate this 28-day vaccination interval, and to restore the objectives associated with this interval. The original 28-day interval target group was 75 participants. Hence the total number of placebo recipients from Groups 6, 8 and 10 (target n 75) is intended to fulfill the original target enrollment for Group 7.

Four dose levels will be evaluated: 1×10^{11} vp, 5×10^{10} vp, 2.5×10^{10} vp, and 1.25×10^{10} vp.

- The evaluation of the 2.5×10^{10} vp vaccine dose level will provide insight (immunogenicity) in the possibility to use this dose level for dose sparing.
- The evaluation of the 1.25x10¹⁰ vp vaccine dose level will allow for the assessment of immunogenicity of this dose level which is representative of the vaccine titer of the 5x10¹⁰ vp dose level at the end of the foreseen shelf-life in the context of emergency use with storage at 2-8 °C.

By lowering the dose level (ie, to 2.5×10^{10} vp and 1.25×10^{10} vp), there will also be a potential to immunobridge to a lower dose level regimen, should the efficacy study (VAC31518COV3001) provide evidence of an immune correlate of protection.

The regimen is selected based on previous preclinical and clinical data from other Ad26-based vaccines.

Note that 2 clinical studies, VAC52150EBL3002 (Ebola) and IPCAVD001 (HIV), showed that Ad26-based vaccines induce a potent humoral and cellular immune response at doses equivalent or lower than 1.25x10¹⁰ vp.

Adolescents

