6. STUDY VACCINATION AND CONCOMITANT THERAPY

6.1. Study Vaccinations Administered

Ad26.COV2.S (also known as Ad26COVS1) will be supplied at a concentration of $1x10^{11}$ vp/mL and $2x10^{11}$ vp/mL as a suspension in single-use vials, with an extractable volume of 0.5 mL. Formulation buffer will be supplied as diluent as 15 mM citrate, 5% (w/w) hydroxypropyl- β -cyclodextrin, 0.4% (w/w) ethanol, 0.03% (w/w) polysorbate 80, 75 mM NaCl, pH 6.2, and placebo will be supplied as a 0.9% NaCl solution.

Adult participants in Groups 1-6 will be vaccinated on Day 1 and Day 57, in Groups 7-8 on Day 1 and Day 29, in Groups 9-10 on Day 1 and Day 85.

Adolescent participants in Groups A-B will be vaccinated with a single dose of Ad26.OV2.S at 2.5×10^{10} vp on Day 1. Adolescent participants in Group C who received placebo on Day 1 will receive a single dose of Ad26.OV2.S at 2.5×10^{10} vp following unblinding at approximately 6 months of study participation.

A volume of 0.5 mL will be administered to all (adult and adolescent) participants.

• Ad26.COV2.S:

 $1x10^{11}$ vp dose level (Adult Group 4): 0.5 mL is withdrawn from one vial containing 0.75mL $2x10^{11}$ vp/mL.

 $5x10^{10}$ vp dose level (Adult Groups 1, 5, 7, 9): 0.5 mL is withdrawn from one vial containing 0.75 mL $1x10^{11}$ vp/mL.

 2.5×10^{10} vp dose level (Adult Group 2, and Adolescent Groups A, B and C): 0.75 mL of formulation buffer is added to a vial containing 0.75 mL 1×10^{11} vp/mL, providing 5×10^{10} vp/mL in a vial with an extractable volume of more than 1 mL. Then 0.5 mL will be withdrawn from this vial.

 1.25×10^{10} vp dose level (Adult Group 3 and antigen presentation in Groups 1-5, 7 and 9): 0.4 mL is withdrawn from one vial containing 0.75 mL 1×10^{11} vp/mL and added to a vial containing 1.2 mL formulation buffer, providing 2.5×10^{10} vp/mL in a vial with an extractable volume of more than 1 mL. Then 0.5 mL will be withdrawn from this vial.

• Placebo: 0.9% NaCl solution (Groups 6, 8, and 10): 0.5 mL

Study vaccine will be administered by IM injection into the deltoid muscle, preferably of the non-dominant arm. Subsequent vaccinations are preferably administered in the opposite arm. If an injection cannot be given in the deltoid muscle due to a medical or other contraindication (for

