9.2.1. Immunogenicity

The primary objective in the adult population of the study is to explore the dose-response and interval-response relationship of humoral immune responses induced by different dose levels and different vaccine administration timings of Ad26.COV2.S using VNA titers and ELISA U/mL.

To explore the dose-response relationship between VNA/ELISA and different dose levels of the Ad26.COV2.S vaccine, a separate linear regression model will be fitted for:

- all active groups 14 days post vaccination 1
- all active groups 28 days post vaccination 1
- the 2-dose active groups using data of Groups 1-3, 28 days post vaccination 2
- the single-dose active groups using data of Groups 4-5, 28 days post vaccination 2
- the 2-dose active groups, using data of groups 1-3, 14 days post vaccination 2

In the linear regression model the log transformed VNA/ELISA titers at each timepoint will be used as dependent variable and the dose levels as independent variable.

Depending on the model fit, other models (eg, log-linear models or EMAX models) may be explored as well for the 56-day interval regimen.

Details on the comparison between the different dose levels and vaccination interval groups will be outlined in the SAP.

9.2.2. **Safety**

Placebo recipients are included for blinding and safety purposes and will provide additional control specimens for the immunogenicity assays.

While mild to moderate vaccine reactions (local site and systemic responses) are expected, AEs that preclude further dose administration or more serious ones that would limit product development are not anticipated. The observation of 0 events (eg, SAEs) is associated with 95% confidence that the true event rate is below the rates specified in Table 9 for the considered number of participants.

Table 9: Upper Limit of the 95% One-sided Confidence Interval if no Cases are Observed for Different Sample Sizes

Sample Size	N=25	N=50	N=75	N=150
Upper Limit 95% one- sided CI	11.3%	5.8%	3.9%	2.0%

CI = confidence interval, N = number of participants

Table 10 provides the probability of observing at least one AE in a group of the considered sample size given several true AE rates.

True AE Rate	Probability of Observing at Least One AE in N Participants (%)				
(%)	N=25	N=50	N=75	N=150	
0.5	12	22	31	53	
1	22	39	53	78	
2.5	47	72	85	98	
10	93	99	>99.9	>99.9	
25	>99.9	>99.9	>99.9	>99.9	
50	>99.9	>99.9	>99.9	>99.9	

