5.1.5. Analyses by groups and pooled across groups

All analyses are planned to be performed within each group separately, unless explicitly indicated that data will be pooled across groups.

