5.7.1.5. Immunogenicity against the insert

5.7.1.5.1. Humoral assays

For VNA (both wild-type virus and pseudovirion expressing S protein, as available), the following statistics will be calculated: N, geometric mean and corresponding 95% CI of the actual values, fold increase from baseline, fold increase from pre-dose 2 (for time points after dose 2), fold increase from pre-antigen presentation (for time points after the antigen presentation), difference to Ad26 5e10: GMR (95% CI) for Geometric mean and GMR (95% CI) for Geometric mean increase from Baseline.

For the calculation of the geometric mean and its corresponding 95% CI, the arithmetic mean and its corresponding 95% CI are calculated on the \log_{10} transformed values. These values are back transformed to provide the geometric mean and its corresponding 95% CI.

For wild-type and pseudovirion VNA separately:

- A sample will be considered positive if the value is strictly greater than the LLOQ (>LLOQ).
- Responder definition. A post-baseline sample will be considered a responder if at least one of the following conditions is satisfied:
 - The baseline sample value is less than or equal to the LLOQ (\leq LLOQ) and the post-baseline sample value is strictly greater than the LLOQ (>LLOQ)
 - The baseline sample value is strictly greater than the LLOQ (>LLOQ) and the post-baseline value represents an at least 4-fold (\geq 4-fold) increase from the baseline sample value.

Actual values are tabulated and shown as dot plots with dots for participant values, and the corresponding geometric mean and 95% CI per time point for each assay. In addition, GMT plots over time, combining the regimens in one graph (without individual participant dots) will also be generated.

Participant profiles of the actual values over time will be graphically presented.

Reverse distribution curves of the actual values are provided for selected time points.

In the graphs, original values will be displayed on the \log_{10} scale.

Further details and/or updated rules will be provided in the DPS.

For **S-ELISA**, the same as above applies.

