6.2. Appendix 2 Changes to Protocol-Planned Analyses

In October 2020, the current study was temporarily paused because one of the pausing rules was met in study COV3001. When the pause was lifted, most of the participants in Groups 7-8 had missed their visit window for Vaccination 2, rendering the intent of the 28-day vaccination interval in these groups futile.

For safety analyses,

- the 2 subjects vaccinated before pausing rule (28-day interval) will only be shown in the listings.
- the other subjects received the vaccination 2 between 51 and 72 days after Vaccination 1. They will be integrated in the Full Analysis Set with groups 1 and 6 (56-day interval).

For immunogenicity analyses,

- subjects randomized in groups 7 and 8 won't be included in PPI set
- a modified PPI set will be defined as follows :
subjects with vaccination 2 within the window (54-64) or subjects who did not receive vaccination 2 will be integrated in groups 1 and 6
- a modified FAS set will be defined as follows :
subjects in mPPI set and subjects with vaccination 2 in (51-53) days or (65-72) days window

6.3. Appendix 3 Guidance for Industry: Toxicity Grading Scale for Healthy Adult and Adolescent Volunteers Enrolled in Preventive Vaccine Clinical Trials

The laboratory values provided in the tables below serve as guidelines and are dependent upon institutional normal parameters. Institutional normal reference ranges should be provided to demonstrate that they are appropriate.

If a laboratory value falls within the grading as specified below but also within the local laboratory normal limits, the value is considered as normal.

Serum *	Mild (Grade 1)	Moderate (Grade 2)	Severe (Grade 3)	Potentially Life Threatening (Grade 4)**
Sodium – Hyponatremia mEq/L	132 – 134	130 – 131	125 – 129	< 125
Sodium – Hypernatremia mEq/L	144 – 145	146 – 147	148 – 150	> 150
Potassium – Hyperkalemia mEq/L	5.1 – 5.2	5.3 – 5.4	5.5 – 5.6	> 5.6
Potassium – Hypokalemia mEq/L	3.5 – 3.6	3.3 – 3.4	3.1 – 3.2	< 3.1
Glucose – Hypoglycemia mg/dL	65 – 69	55 – 64	45 – 54	< 45
Glucose – Hyperglycemia Fasting – mg/dL Random – mg/dL	100 – 110 110 – 125	111 – 125 126 – 200	>125 >200	Insulin requirements or hyperosmolar coma
Blood Urea Nitrogen BUN mg/dL	23-26	27 – 31	> 31	Requires dialysis
Creatinine – mg/dL	1.5 – 1.7	1.8 – 2.0	2.1 – 2.5	> 2.5 or requires dialysis
Calcium – hypocalcemia mg/dL	8.0 – 8.4	7.5 – 7.9	7.0 – 7.4	< 7.0
Calcium – hypercalcemia mg/dL	10.5 – 11.0	11.1 – 11.5	11.6 – 12.0	> 12.0

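### The SAP's only pairwise immunogenicity contrast is a GMR to an unspecified 5×10¹⁰ vp regimen; the reference group and time point should be named for each contrast

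*SAP*

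**What the plan says.** Protocol 9.2.1 hands the matter to the SAP: "Details on the comparison between the different dose levels and vaccination interval groups will be outlined in the SAP". In SAP 5.7.1.5.1 the list of statistics for VNA, applied equally to S-ELISA, ends with "difference to Ad26 5e10: GMR (95% CI) for Geometric mean and GMR (95% CI) for Geometric mean increase from Baseline". It gives no group number, number of doses, interval or time point for the reference.

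Protocol 6.1 lists the 5×10¹⁰ vp "dose level (Adult Groups 1, 5, 7, 9") as four groups. By protocol Table 2 these are Group 1 (two doses, 56 days apart), Group 5 (one dose, then placebo on Day 57), Group 7 (two doses, planned 28 days apart) and Group 9 (two doses, 84 days apart). SAP Appendix 2 changes this after the October 2020 pause: "subjects randomized in groups 7 and 8 won't be included in PPI set". In the modified PPI set, those whose second vaccination fell in the 54–64 day window, or who had none, join Groups 1 and 6.

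SAP 5.1.5 sets the default on pooling: "All analyses are planned to be performed within each group separately, unless explicitly indicated that data will be pooled across groups". The GMR text contains no such indication.

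The SAP has other between-regimen analyses, all on named groups. Section 5.7.1.6.1 regresses log10 VNA and ELISA on dose: Groups 1–10 at 14 and 28 days after Vaccination 1, and, at 28 days after Vaccination 2, Groups 1–3 with 6 and Groups 4–5 with 6. Section 5.7.1.6.2 regresses on interval using Groups 3, 7 and 9. Section 5.7.1.5.1 also displays Group 4 beside the lower two-dose regimens descriptively. Section 5.7.1.6 calls the modelling exploratory, and no hypothesis is tested.

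**The concern.** The dose question is a stated purpose of the trial. Protocol 4.3 says of 2.5×10¹⁰ vp that evaluating this "vaccine dose level will provide insight (immunogenicity) in the possibility to use this dose level for dose sparing". A reader of the results tables will look for the ratio of that regimen to the 5×10¹⁰ vp regimen, and the plan does not say which one that is.

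The consequence depends on the time point. Before Vaccination 2, Groups 1 and 5 have had the same injection and follow the same visit schedule, so either is a fair reference. The default against pooling then leaves a choice of one, or two GMRs for the same contrast, each less precise than it need be. After Vaccination 2 the candidates are different regimens, and a ratio to the wrong one carries a number-of-doses or interval effect as well as a dose effect.

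The interval question is affected too. The one planned interval model combines Group 3, a 1.25×10¹⁰ vp group, with Groups 7 and 9 at 5×10¹⁰ vp, and Group 7 is not in the PPI set. The natural same-dose comparison, Group 9 with Group 1, is not named anywhere.

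**Working it through.** **The plan's own figures.** The documents give no SD, GMT, margin or power for immunogenicity. The numerical support for group size is the zero-event limit in protocol Table 9. 1 − 0.05^(1/n) gives 11.29%, 5.82%, 3.92% and 1.98% for n = 25, 50, 75 and 150, matching the printed 11.3%, 5.8%, 3.9% and 2.0%. It does not bear on the GMR.

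**Inputs from the documents.** Groups 1–5 have 75 each ("400 participants (75 participants per active vaccine group, 25 in the placebo group")). Group 9 has 50 ("75 participants (50 participants in the active vaccine group, 25 in the placebo group")).

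**Assumptions, not in the documents.** A common log10 SD of 0.3 to 0.6; h, the Group 2/Group 1 GMT ratio, of 0.6 to 0.9; b, the Group 1/Group 5 GMT ratio after Vaccination 2, of 1 to 3.

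**Formula.** The 95% CI is GMR ×/÷ 10^(1.96 × SD × √(1/n₁ + 1/n₂)).

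**After Vaccination 1: precision.** With one reference group the variance multiplier is 1/75 + 1/75 = 0.0267. With Groups 1 and 5 pooled it is 1/75 + 1/150 = 0.0200. The ratio is 0.75, so variance falls 25%. √0.75 = 0.866, so the log CI width falls 13%. These percentages need only the planned group sizes and equal SDs. At SD 0.45 the CI factor goes from 1.39 to 1.33.

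**After Vaccination 2: direction.** The GMR of Group 2 to Group 1 is h; to Group 5 it is h × b. The point estimates straddle 1 only when h < 1 < h × b, that is when b > 1/h. For h = 0.7, b must exceed 1/0.7 = 1.43.

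| SD | h | b | Group 2 v Group 1 | Group 2 v Group 5 |
|---|---|---|---|---|
| 0.4 | 0.7 | 1.0 | 0.70 (0.52–0.94) | 0.70 (0.52–0.94) |
| 0.4 | 0.7 | 1.5 | 0.70 (0.52–0.94) | 1.05 (0.78–1.41) |
| 0.4 | 0.7 | 2.0 | 0.70 (0.52–0.94) | 1.40 (1.04–1.88) |
| 0.5 | 0.7 | 2.0 | 0.70 (0.48–1.01) | 1.40 (0.97–2.02) |
| 0.6 | 0.7 | 2.0 | 0.70 (0.45–1.09) | 1.40 (0.90–2.18) |

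In these rows, only the third has both intervals excluding 1 in opposite directions. In the last two, only the point estimates differ in direction. With b = 1 nothing reverses.

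**What the regression offers.** For Groups 1–3 with 75 each, linear in dose (1.25, 2.5, 5; mean 2.917), the sum of squares is 75 × (2.778 + 0.174 + 4.340) = 546.9. The SE of the log10 ratio of 2.5 to 5 is 2.5 × SD/√546.9 = 0.107 SD. The pairwise GMR has 0.163 SD. If the linear form holds, the regression is the more precise of the two.

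**Interval.** In the PPI set the Groups 3, 7 and 9 model reduces to Group 3 (1.25×10¹⁰ vp, 56 days) and Group 9 (5×10¹⁰ vp, 84 days). Dose and interval change together, so they cannot be separated. Group 9 v Group 1 holds dose at 5×10¹⁰ vp. Its multiplier is √(1/50 + 1/75) = 0.183, giving a CI factor of 1.45 at SD 0.45.

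**The case against.** The strongest reply is that the regressions are the main method. Protocol 9.2.1 and SAP 5.3.1 describe the adult immunogenicity objective as exploring dose-response and interval-response, and SAP 5.7.1.6.1 assigns named groups to the dose models. The Groups 1–3 model addresses dose on the same schedule, and the post-Vaccination 1 model already uses Groups 1 and 5 together. The GMR is one entry in a list of descriptive statistics. This stands. A reader might infer that the dose question has no planned comparison, or that post-Vaccination 1 precision is lost throughout; the documents do not support either. What remains is that the model form, and whether placebo is kept, depend on the data, and that no 2.5 v 5×10¹⁰ vp estimate is specified from the model.

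A second reply is that each group's geometric mean and CI are tabulated, and that SAP 5.7.1.5.1 leaves further details to the Data Presentation Specifications, which may name the reference. That document is not available here, so this cannot be excluded. Merely naming the reference could therefore be treated as pending detail. But the protocol assigned the comparison to the SAP, and group-level unblinded data reach the sponsor at the interim and primary analyses (protocol 9.5), so the SAP is the better place to fix it. The pooled reference also needs an explicit indication, given SAP 5.1.5.

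**Conclusion.** The point holds as a modest, cheap improvement. The GMR reference is not identified: four randomised groups fit the label, three in the PPI set.

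After Vaccination 1 the cost is duplicate GMRs and an avoidable loss of precision in that output (variance 25%, log CI width 13%, assuming equal SDs and the planned group sizes). The choice of reference does not bias the dose contrast there.

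After Vaccination 2 the cost is interpretive: the ratio can mix dose with number of doses or interval. A reader might go further and infer that the same data could show a lower-dose regimen as both inferior and superior to 5×10¹⁰ vp. The documents do not support that. They set no hypothesis, margin or decision rule. A reversal of point estimates requires b > 1/h, which is an assumption, and CIs excluding 1 on both sides require a favourable SD as well. A ratio to a two-dose regimen and a ratio to a one-dose regimen also answer different questions.

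The gap in the interval comparison depends on no assumed value: on the PPI set the planned model confounds dose with interval.

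**What to change.** In SAP 5.7.1.5.1, replace the unspecified reference with named GMR contrasts for VNA and S-ELISA:

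- **Days 15 and 29, before Vaccination 2:** Groups 2, 3 and 4 each against Groups 1 and 5 pooled, stated as an explicit exception to SAP 5.1.5.
- **14 and 28 days after Vaccination 2:** Groups 2 and 3 each against Group 1 (same schedule, dose only), and Group 4 against Group 5 (single dose). Label any contrast of a two-dose regimen with Group 5 as supportive.
- **Interval:** Group 9 against Group 1, at the same dose. Protocol 4.1 speaks of assignment to one of ten groups but gives Groups 1–6 and 9–10 separate ratios, so state whether this contrast lies within one randomisation.

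Reconcile the group list in SAP 5.7.1.6.2 with Appendix 2, since Group 3 differs in dose from Groups 7 and 9 and Group 7 is outside the PPI set. Add a sentence on how the Groups 1–3 regression informs the dose-sparing question.

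The cost is one SAP paragraph and a table shell. No new data are collected; the sponsor gives up only the freedom to pick the reference later.

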- Participant has a history of an underlying clinically significant acute or chronic medical condition or physical examination findings for which, in the opinion of the investigator, participation would not be in the best interest of the participant (eg, compromise the wellbeing) or that could prevent, limit, or confound the protocol-specified assessments.
- Participant had surgery requiring hospitalization (defined as inpatient stay for longer than 24 hours or overnight stay), within 12 weeks before vaccination, or will not have fully recovered from surgery requiring hospitalization, or has surgery requiring hospitalization planned during the time the participant is expected to participate in the study or within 6 months after the last dose of study vaccine administration.
- 13 Participant has a contraindication to IM injections and blood draws eg, bleeding disorders.
- 14 Criterion Deleted per Amendment 4.
 - 14.1 Criterion reinstated per Amendment 5:

Participant is an employee of the investigator or study site, with direct involvement in the proposed study or other studies under the direction of that investigator or study site, as well as family members of the employees or the investigator, or an employee of the sponsor.

15 Participant has chronic active hepatitis B or hepatitis C infection per medical history.

- 16 Participant has had major psychiatric illness or drug or alcohol abuse which in the investigator's opinion would compromise the participant's safety or compliance with the study procedures.
- 17 Participant cannot communicate reliably with the investigator.
- Participant who, in the opinion of the investigator, is unlikely to adhere to the requirements of the study or is unlikely to complete the full course of vaccination and observation.
- 19 Participant previously received a coronavirus vaccine.
- 20 Participant has a positive diagnostic test result for past (serological testing) or current (PCR based viral RNA detection) SARS-CoV-2 infection at screening.
- 21 Criterion modified per Amendment 1:
 - 21.1 Criterion modified per Amendment 3:

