5. STATISTICAL ANALYSES

5.1. General Considerations

5.1.1. Study phases

A baseline (or reference) value will be defined as the value of the last available assessment prior to the first vaccination on Day 1.

The safety analysis will present all results by phase (cf. section 5.1.2 for phase definitions). Immunogenicity results will be presented per scheduled time point as appropriate. Listings will be shown per phase and time point.

Study day or relative day is defined as follows:

Study Day = visit date - date of Day 1 + 1; if visit date \geq date of Day 1 (date of first vaccination).

Study Day = visit date - date of Day 1; if visit date $<$ date of Day 1 (date of first vaccination).

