5.4. Secondary Endpoint(s) Analysis

5.4.1. Key/Confirmatory Secondary Endpoint(s)

The secondary endpoints in this study, are:

Adults

Anamnestic response to antigen presentation of Ad26.COV2.S at the 1.25×10^{10} vp dose level, administered 4 months after Vaccination 2 (2-dose schedule) or 6 months after a Vaccination 1 (single-dose schedule), 7 days after antigen presentation:

- Serological response to vaccination as measured by VNA titers and ELISA (S-ELISA, ELISA U/mL [EU/mL]), 7 days after antigen presentation.
- Antibody GMTs (VNA) and GMCs (S-ELISA), 7 days after antigen presentation.

Safety and Reactogenicity of antigen presentation of Ad26.COV2.S:

- Solicited local and systemic AEs for 7 days after antigen presentation

- Unsolicited AEs for 28 days after antigen presentation
- SAEs and adverse events of special interest (AESIs) throughout the study (from after antigen presentation until end of the study)

Humoral Immune Response across all groups, at all blood collection timepoints.

- Neutralizing antibody titers to the wild-type SARS-CoV-2 virus expressing S protein as measured by VNA, at all blood collection timepoints.
- Binding antibody titers to SARS-CoV-2 or individual SARS-CoV-2 proteins (e.g., S protein) as measured by ELISA, at all blood collection timepoints.

Adolescents

Humoral immune response to a single dose of Ad26.COV2.S at the 2.5×10^{10} dose level, administered IM.

- Serological response to vaccination as measured by VNA titers and ELISA (S-ELISA, EU/mL), 28 days after vaccination.
- Antibody GMTs (VNA) and GMCs (S-ELISA), 28 days after vaccination.

Humoral immune response to Ad26.COV2.S at the 2.5×10^{10} dose level, at all blood collection timepoints.

- Neutralizing antibody titers to the wild-type SARS-CoV-2 virus expressing S protein as measured by VNA, at all blood collection timepoints.
- Binding antibody titers to SARS-CoV-2 or individual SARS-CoV-2 proteins (eg, S protein) as measured by ELISA, at all blood collection timepoints.

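### The SAP's only responder rule is tied to Day 1, so the response rate 7 days after antigen presentation counts persisting antibody and does not by itself measure recall

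*SAP*

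**What the plan says.** The adult secondary objective in SAP 5.4.1 is introduced as "Anamnestic response to antigen presentation of Ad26.COV2.S at the" 1.25×10^10 vp dose level. It has two immunogenicity endpoints: "Serological response to vaccination as measured by VNA titers and ELISA (S-ELISA, ELISA U/mL [EU/mL]), 7 days after antigen presentation" and "Antibody GMTs (VNA) and GMCs (S-ELISA), 7 days after antigen presentation". SAP 5.4.1.1 gives no definition of its own and points to 5.7.1.

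The only responder rule there is in 5.7.1.5.1: "Responder definition. A post-baseline sample will be considered a responder if at least one of the following conditions is satisfied". The two conditions are:

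- baseline at or below LLOQ and the later sample above LLOQ; or
- baseline above LLOQ and at least a 4-fold rise from it.

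The section carries the rule over to S-ELISA. SAP 5.1.1 fixes the reference: "A baseline (or reference) value will be defined as the value of the last available assessment prior to the first vaccination on Day 1".

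The same section also plans, for VNA and S-ELISA, a fold increase from the pre-antigen-presentation value at time points after antigen presentation. The Schedules of Activities (Protocol 1.3.1 to 1.3.3) draw 10 mL of serum before that injection: Visit 10 in Groups 1-5, Visit 8 in Group 7 and Visit 9 in Group 9.

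**The concern.** Adults are excluded under Protocol 5.2.1 if "Participant has a positive diagnostic test result for past (serological testing) or current (PCR based viral RNA detection) SARS-CoV-2 infection at screening". Most participants should therefore start at or below LLOQ, and for them being a responder reduces to having any sample above LLOQ. A participant who carries antibody from the primary regimen into Injection 3 is then a responder 7 days later with a flat titre, or with a falling one that stays above LLOQ.

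The design offers no other way to separate the two. In Protocol Table 2 every vaccine-primed group receives 1.25×10^10 vp at Injection 3, and only the placebo-primed groups receive placebo. A gap in response rates between active and placebo groups would appear from priming alone. The pre-injection sample is the one available reference, and the responder rule does not use it. At stake is a persistence rate being reported as the serological response for the anamnestic objective.

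**Working it through.** The plan states no response rate, power or threshold for this endpoint, so there is no figure of its own to reproduce.

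**Step 1, from the definitions.** With Day 1 at or below LLOQ, responder means sample above LLOQ. If a share q is above LLOQ just before Injection 3 and titres do not fall, the 7-day rate is at least q with zero recall. For assumed q = 70%, 85%, 95%, that is at least 70%, 85%, 95%.

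**Step 2, an illustration.** Assumptions, none from the documents: Day 1 at or below LLOQ; pre-injection geometric mean R × LLOQ; between-participant SD S on the log10 scale; true recall fold F. The rate under the SAP rule is Φ(log10(R·F)/S). For example, with R = 2, S = 0.5, F = 1: Φ(0.301/0.5) = Φ(0.602) = 72.6%.

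| R | S | Before injection, and 7 days after with no recall | 7 days after a true 4-fold rise |
|---|---|---|---|
| 2 | 0.3 | 84.2% | 99.9% |
| 2 | 0.5 | 72.6% | 96.5% |
| 5 | 0.3 | 99.0% | 100.0% |
| 5 | 0.5 | 91.9% | 99.5% |
| 10 | 0.3 | 100.0% | 100.0% |
| 10 | 0.5 | 97.7% | 99.9% |

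For R of 5 or more, a true 4-fold rise moves the rate by at most 99.5 − 91.9 = 7.6 points. For R = 2 it moves by 15.7 points (S = 0.3) or 23.9 points (S = 0.5).

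**Step 3, a rule referenced to the pre-injection sample.** Let w be the within-participant assay SD, assumed 0.1 to 0.2 log10. The 4-fold condition alone is met with probability Φ((log10 F − log10 4)/(√2·w)): 0.0-1.7% at F = 1, 50% at F = 4, 86-98% at F = 8.

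The full two-part rule also counts a move from at or below LLOQ to above it, which assay noise alone can produce. With no recall, that chance is P(pre ≤ LLOQ, post > LLOQ) for a bivariate normal with both means log10 R (LLOQ at 0), variances S² + w² and covariance S². Over the same R, S and w it is 0.0-8.9%, largest at R = 2, S = 0.3, w = 0.2. By simulation, the whole two-part rule gives 0-10% with no recall, 50-58% at F = 4 and 86-98% at F = 8.

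**Step 4, the statistic already planned.** I simulated the geometric mean fold increase from pre-antigen presentation with values floored at LLOQ, w = 0.15 and, where there is recall, a between-participant SD of 0.25 log10 in the fold. It is 1.00 with no recall and 3.4-4.0 with a true 4-fold rise. It does separate recall from persistence.

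**The case against.** A reader might infer that the SAP cannot show an anamnestic response at all. The documents do not support that. The fold increase from the pre-injection sample is a direct measure of recall and is planned for both assays. Results are presented by scheduled time point, so a pre-injection rate tabulated beside an unchanged 7-day rate would expose persistence. Geometric means and participant profiles over time are planned too.

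Nor do the documents support saying that the rate will sit near its ceiling in every group. They give no share above LLOQ before Injection 3, and they do not equate the screening serology test with the VNA or S-ELISA LLOQ.

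Protocol 9.4.2 promises several definitions of serological response expressed as fold increases, and SAP 5.7.1.5.1 leaves updated rules to the Data Presentation Specifications. That leaves room for another rule, but none is written in the SAP, and an endpoint definition belongs there.

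A 4-fold threshold at 7 days is also not justified anywhere in the documents, and a continuous fold increase avoids dichotomising. This stands as a caution about the replacement rule. It does not make the Day 1 rate a measure of recall.

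**Conclusion.** The point holds for the binary endpoint only. Followed as written, the serological response rate 7 days after antigen presentation describes antibody above LLOQ relative to Day 1, and read alone it says little about recall. The geometric mean fold increase from pre-antigen presentation answers the objective, with two gaps: the LLOQ and ULOQ imputation in SAP 5.7.1.2 is written only for fold increases from baseline, and the between-group GMRs in 5.7.1.5.1 cover the geometric mean and the increase from baseline but not the increase from the pre-injection value.

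The size is not known from the documents. Under the assumed titres above, the rate with no recall is about 73-100%. Severity is moderate: SAP 5.7.1.4 tests no hypothesis, and no sample size or error rate depends on this percentage.

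**What to change.** In SAP 5.7.1.5.1, for time points after antigen presentation, add a responder rate referenced to the pre-antigen-presentation sample with the SAP's existing thresholds: pre-injection at or below LLOQ and post above LLOQ, or pre-injection above LLOQ and at least a 4-fold rise from it. Show the two components separately, because the first is sensitive to assay noise near LLOQ.

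Extend the imputation rule in 5.7.1.2 and the between-group GMR to the fold increase from pre-antigen presentation. Keep the Day 1-referenced rate at these visits, labelled as response relative to Day 1 (seropositivity) and not as anamnestic response.

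The cost is SAP wording, one derived variable and some extra table rows; no new samples are needed. The reported response rate will be lower, and capping at ULOQ may hide some rises in participants with high pre-injection titres, so the number at ULOQ should be shown alongside.
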